The total symptom score, the 6 domain symptom scores, and the 3 component symptom scores will be summarized by treatment group at each visit (including change from baseline and percent change from Baseline to each visit), including the combined low-dose and high-dose VIS410 group with n, mean, SD, median, minimum, and maximum by treatment group, including a combined low-dose and high-dose VIS410 group.

The count and percentage of subjects with a mean score ≤ 1.0 for the total symptom score, 6 domain symptom scores, and 3 component score will be summarized at each post-baseline visit. An additional summary of counts and percentages of subjects with a score of 0 or 1 for all of the individual symptom scores composing the total symptom score, 6 domain symptom scores, and 3 component symptom scores will also be presented for each post-baseline visit. These summaries will also be presented by region: USA, South Africa, and the rest of the world.

Area under the curve (AUC) for the total symptom score, 6 domain symptom scores, and 3 component symptom scores will be calculated using the linear trapezoidal rule, i.e. $AUC_{t_i, t_{i+1}} = 1/2 * (S_i + S_{i+1}) * (t_{i+1} - t_i)$ where S_i is the total symptom score at time point t_i . All time points from pre-dose to Day 10 will be considered.

A sensitivity analysis of the total symptom score, domain symptom scores, and component symptom scores will be conducted by repeating the above analysis in the mITT population,

excluding subjects who received antiviral therapy for influenza during the first 10 days of the study. Determination of applicable antiviral therapy for influenza will be defined before the study is unblinded.

Additional exploratory analysis, including but not limited to evaluation of sums instead of means of symptom scores, may be performed for the total symptom score, 6 domain symptom scores, and 3 component symptom scores.

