11.2 Nasopharyngeal Viral Load

Standard non-compartmental approaches using Phoenix WinNonlin (Pharsight Corporation, Princeton, NJ, USA; Version 7.0 or higher) will be used to calculate peak viral load (VL) and the area under the viral load-time curve (VL AUC). Viral load at each study visit, proportion of subjects with negative results at each study visit, peak VL, and VL AUC based on qRT-PCR and TCID₅₀ from nasopharyngeal secretions will be summarized with n, mean, SD, geometric mean, CV, minimum and maximum values in the mITT population overall and per influenza A virus subtype. All available viral data within the mITT population will be assessed to calculate proportion of subjects with negative results at each study visit. For all other calculated parameters, viral load will be assessed on all samples in the mITT population collected through the Day 7 visit. In addition, VL and VL AUC for the first 50 subjects will be listed through Day 14 (no summary statistics will be presented). For missing data on Day 3, Day 5 and Day 7, the analysis will be conducted without imputation and with the last observable measurement carried forward (LOCF). For missing data on Day 1, the analysis will be conducted by replacing the missing data with the Day 3 observable measurement. Subjects missing both Day 1 and Day 3 virology data will be removed from the analysis.

A t-test will be used to assess the difference between treatment groups in the VL AUC and peak VL from nasopharyngeal swabs based on qRT-PCR and TCID₅₀. If the assumptions needed for the t-test are not met, log transformation and/or non-parametric methods will be used.

Chi-square methods will be used to compare differences in treatment groups relative to placebo for the proportion of subjects with negative results on Day 3, Day 5 and Day 7 study visits.

A sensitivity analysis will also be performed; the data summary will be repeated in the mITT population excluding subjects who received antiviral therapy during the study. Determination of applicable antiviral therapy will be defined before the study is unblinded. All viral load data generated per the analytical plan will be listed.

For the influenza A virus subtype H3, virus load data measured by TCID₅₀ will be read out by both hemagglutination and NP-ELISA. The sensitivity is higher for NP-ELISA; therefore, all viral load parameters will be calculated using the data from NP-ELISA only.

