11.3 Time to Resolution of Viral Load

Median time to cessation of viral shedding, determined by qRT-PCR and TCID₅₀ results, and the 95% CI about the median, will be presented for each treatment group. This analysis will use Kaplan-Meier methods. Additional exploratory statistical analyses may be conducted as appropriate. Time to resolution of viral load will be assessed on all samples in the mITT population collected through the Day 7 visit. For missing data on Day 3, Day 5, and Day 7, the analysis will be conducted without imputation and with the last observable measurement carried forward (LOCF). For missing data on Day 1, the analysis will be conducted by replacing the missing data with the Day 3 observable measurement. Subjects missing both Day 1 and Day 3

virology data will be removed from the analysis. Resolution of viral load is considered to be one BLQ or lower measurement with no samples following that which are greater than the BLQ.

The following virology parameters will be derived:

- Time to resolution of viral shedding from end of infusion
 - Number of days from end of infusion until virus is no longer detectable (at or below the limit of detection) with no samples following that are greater than the BLQ through Day 7 visit
 - If virus is still above level of detection at the end of the study, the last day of viral collection through Day 7 visit will be used
- Time to resolution of viral shedding from onset of symptoms
 - Number of days from onset of symptoms until virus is no longer detectable (at or below the limit of detection) with no samples following that are greater than the BLQ through Day 7 visit
 - If virus is still above level of detection at the end of the study, the last day of viral collection through Day 7 visit will be used

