16 APPENDICIES

16.1 Changes to the Protocol Specified analyses

ADA data at Day 14 will not be analyzed.

Nasopharyngeal viral load samples will only be analyzed for qPCR and TCID₅₀ until Day 7, unless still positive on Day 7, and then samples will also be analyzed on Day 14. No PCR or TCID₅₀ samples are planned to be analyzed post-Day 14.

QTcF interval prolongation categories were updated to <450, >450 to ≤480, >480 to ≤500, and >500 msec and categories for QTcF increases were updated to <30, >30 to ≤60 and >60 msec from Baseline.

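### The viral-load sensitivity analysis excludes subjects for antiviral use at any time in the study, although its parameters use samples through the Day 7 visit and none are planned for analysis after Day 14

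*SAP*

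**What the plan says.** The exclusion rule is in SAP 11.2: "the data summary will be repeated in the mITT population excluding subjects who received antiviral therapy during the study". It sets no time limit. The protocol synopsis (Study Duration) and Protocol 8.1 put the end of each subject's study at Day 100. SAP 7 lists influenza antivirals through the same day and links that listing to the FluPRO and viral shedding sensitivity analyses.

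The data windows are much shorter:

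- **Viral load by visit, peak viral load, viral-load AUC** (SAP 11.2): "For all other calculated parameters, viral load will be assessed on all samples in the mITT population collected through the Day 7 visit".
- **Chi-square tests against placebo** (SAP 11.2): "for the proportion of subjects with negative results on Day 3, Day 5 and Day 7 study visits".
- **Time to resolution** (SAP 11.3): "Time to resolution of viral load will be assessed on all samples in the mITT population collected through the Day 7 visit". Section 11.3 states no sensitivity analysis of its own.
- **Descriptive proportion negative** (SAP 11.2), the exception: "All available viral data within the mITT population will be assessed to calculate proportion of subjects with negative results at each study visit". Under SAP 16.1, samples are assayed at Day 14 only for subjects still positive on Day 7, and "No PCR or TCID₅₀ samples are planned to be analyzed post-Day 14".

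The parallel rule for symptoms, in SAP 9.1.1, does carry a limit: "excluding subjects who received antiviral therapy for influenza during the first 10 days of the study". FluPRO is collected through Day 10, so that exclusion window matches its data window.

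**The concern.** A sensitivity analysis of this kind asks one question: is the viral-load comparison distorted by antivirals other than study drug? Only antivirals taken before an analysed sample can cause that distortion. One started afterwards, for example for a reinfection in the second month, cannot change a Day 7 result. As written, it still removes the subject.

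The subject is then selected on something that happens after the outcome was measured. Later antiviral use is likely to follow relapse, worsening or hospitalisation. Relapse/reinfection and influenza complications are themselves secondary endpoints and may differ by arm. If the sensitivity result departs from the main result, the reader cannot tell whether antiviral use confounded the main analysis or the later selection moved the check. Viral AUC, peak viral load and time to resolution are secondary endpoints, and this is the only check on antiviral use planned in SAP 11.2.

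**Working it through.** The plan gives no figure to reproduce: there is no sample-size calculation and no expected rate of antiviral use. The check compares windows and then sizes the consequence under stated assumptions.

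**1. Windows.**

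| Item | Data used | Exclusion window as written |
|---|---|---|
| Viral load by visit, peak, AUC | through the Day 7 visit | whole study, to Day 100 |
| Chi-square tests | Days 3, 5, 7 | whole study, to Day 100 |
| Proportion negative, descriptive | all available; none planned after Day 14 | whole study, to Day 100 |
| FluPRO scores | through Day 10 | first 10 days |

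Days on which antiviral use triggers exclusion but cannot affect a Day 7 result: 100 − 8 + 1 = 93 (92 if the visit falls on Day 8, within its one-day window). Days beyond any nominal sampling day planned for analysis: 100 − 15 + 1 = 86. These are calendar days, not a share of subjects.

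**2. Does another sentence supply the limit?** SAP 11.2 says that the applicable antiviral therapy will be settled before unblinding. SAP 9.1.1 has nearly the same sentence beside its explicit 10-day limit. It therefore reads as a decision about which drugs count, not when they were taken.

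**3. Where the wording came from.** Protocol 9.3.4 (viral shedding) and 9.3.5 (symptoms) both describe an optional exclusion covering the whole course of the study. The SAP narrowed the symptom version and left the viral-load version as it was.

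**4. Precision.** Let q be the share of otherwise retained subjects, equal across arms, whose first antiviral falls after the last analysed sample. The standard error is multiplied by 1/√(1 − q):

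- q = 1%: 1/√0.99 = 1.005, a rise of 0.5%
- q = 5%: 1/√0.95 = 1.026, a rise of 2.6%
- q = 10%: 1/√0.90 = 1.054, a rise of 5.4%

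**5. Selection, worst case.** Suppose viral load is normally distributed and late use in one arm falls exactly on the subjects with the highest values, with none in the other arm. Removing the top fraction q moves that arm's mean by −φ(z)/(1 − q) SD, where z is the 1 − q quantile and φ the normal density. This gives −0.11 SD at q = 5% and −0.20 SD at q = 10%. These illustrate an extreme pattern and are not forecasts.

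**The case against.** The case for leaving the text alone has real weight. The main mITT analysis keeps every subject. SAP 4.1 presents p-values for information only. The study is a safety study, and the SAP follows the protocol's own wording. Antivirals are otherwise excluded and are permitted mainly for worsening or new symptoms (Protocol 6.2 and 6.3), so use should cluster in the acute illness and late first use may be rare. All of this stands, and it limits the size of the point. It does not give a reason to exclude someone for an antiviral that could not have touched the data.

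Some stronger readings are tempting, but the documents do not support them:

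- *That viral load is analysed only through Day 7.* The descriptive proportion negative uses all available data, and subjects still positive on Day 7 are assayed at Day 14. An antiviral started between those visits can affect a summarised Day 14 result.
- *That the exclusion reaches antivirals for other diseases.* SAP 11.2 omits the influenza qualifier, but SAP 7 defines the relevant medications as those taken for influenza.
- *That 93 of 100 days implies a large loss of subjects.* Days are not risk, no late-use rate is given, and the base is the mITT population, which can be smaller than the approximately 150 enrolled.
- *That the symptom and viral-load sets ought to be identical.* Their data windows differ, so their exclusion windows may differ too.

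Excluding subjects for early antivirals is also selection after randomisation. The narrower window does not cure that; it removes only the part that serves no purpose.

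**Conclusion.** The mismatch is in the text: the exclusion runs to the end of the study, while the main viral-load parameters and tests stop at the Day 7 visit and nothing is planned for analysis after Day 14. Later antiviral use removes subjects whose analysed samples it could not have affected, and it does so through events that may differ by arm.

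The effect is confined to one sensitivity analysis of secondary endpoints. The loss of precision is small over the assumed 1% to 10% range of late use. The main gain is interpretability, because a difference between main and sensitivity results would no longer be open to explanation by events after the last analysed sample. Whether late use will in fact differ by arm cannot be known from the documents. This is a minor correction.

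The conclusion rests on reading the rule's reference to the study as running to Day 100, which follows from the study duration and fits SAP 7, and on reading the blinded decision on applicable therapy as one about drugs. If the sponsor already intends a time limit, it need only be written down.

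**What to change.** In SAP 11.2, replace the whole-study wording with a window tied to the data: exclude a subject only if an influenza antiviral was started on or before the last viral sample used for that parameter. In practice:

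- the Day 7 visit swab for viral load by visit, peak viral load, viral-load AUC and the Day 3, 5 and 7 tests;
- the Day 14 sample for the Day 14 proportion negative.

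Add the influenza qualifier so that the sentence agrees with SAP 7 and 9.1.1. Protocol 6 requires dates of administration for all therapies, so a day-level rule needs no new data.

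Keeping these subjects and dropping only the samples taken after the antiviral started may look attractive. I would not do that here without a separate missing-data rule. SAP 11.2 handles missing Day 3, 5 and 7 values both without imputation and by LOCF. The first would shorten the AUC, and the second would carry a pre-antiviral value forward, in subjects selected because they were getting worse.

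The cost is one phrase in the SAP, settled before unblinding. Study conduct, data collection and the main analysis do not change.

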9.2 RANDOMIZATION AND BLINDING

This will be a double-blind study. The Contract Research Organization (CRO) and site study personnel and Visterra personnel will not be aware of which treatment (active study drug or placebo) the subjects have been given. Subjects will not be aware of which treatment they have been administered.

Subjects will be randomized 1:1:1 to receive VIS410 2000 mg, VIS410 4000 mg, or placebo. A randomization list with randomization numbers will be created. The randomization numbers must be used sequentially to ensure an overall balance; no randomization number can be skipped. Allocation of each subject to a given treatment sequence will be described in a randomization list prepared by Visterra or designee. The randomization will be balanced using randomly permuted blocks across the treatment groups.

The randomization list will not be available to the subjects, Investigators, (blinded) monitors, or employees of the clinical center involved in the management of the study before unblinding of the data, unless in case of emergency. The Sponsor's clinical team will also be blinded during the study as they will not have direct access to the randomization list. The CRO performing data management and statistical activities will receive a copy of the randomization list during database lock. Other team members will not have access to any data that could lead to unblinding.

Unblinding of the individual subject's treatment by the Investigator should be limited to medical emergencies or urgent clinical situations in which knowledge of the subject's study treatment is necessary for clinical management. In such cases, the Investigator must first attempt to contact the Medical Monitor or appropriate back up (contact information as detailed in a separate document), to discuss and agree to the need for unblinding to occur. The Medical Monitor or designee will answer calls 24 hours a day, 7 days a week, 365 days of the year. In situations in which the Investigator has tried, but is unable to reach the Medical Monitor, they should use their best judgment, based on the nature and urgency of the clinical situation, and may proceed with unblinding without having successfully reached and discussed the situation with the Medical Monitor.

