- $AUC_{0-\infty}$: area under the serum concentration-time curve from time 0 extrapolated to infinity
- $AUC_{0-\text{last}}$: area under the serum concentration-time curve from time 0 to the last measurable concentration
- $t_{1/2}$: terminal elimination half-life
- CL: total clearance
- V_d : volume of distribution

PK data from this study will be also analyzed by population PK modeling.

Nasopharyngeal Secretion Pharmacokinetics

Nasopharyngeal secretion concentrations and the computed PK parameters will be listed by subject for VIS410. Summary statistics of nasopharyngeal secretion concentrations and PK parameters will be presented including means, geometric means, standard deviations, CV, medians and ranges, as appropriate. Additional analyses and summaries may be generated as appropriate.

The following PK parameters will be determined for VIS410 from nasopharyngeal secretions:

- C_{\max} : maximum concentration observed from nasopharyngeal secretions
- T_{\max} : time of C_{\max}
- $AUC_{0-\infty}$: area under the nasopharyngeal secretion concentration-time curve from time 0 extrapolated to infinity
- $AUC_{0-\text{last}}$: area under the nasopharyngeal secretion concentration-time curve from time 0 to the last measurable concentration
- $t_{1/2}$: terminal elimination half-life
- Ratio of nasal:serum AUC

Additional PK parameters may be determined as appropriate.

9.3.4 *Viral Shedding*

Additional sensitivity analysis may be conducted excluding subjects that received concomitant antiviral therapy during the course of the study.

- One-way analysis of variance (ANOVA) (with treatment group as the factor) or other appropriate statistics detailed in the SAP to assess the difference between VIS410 treatment groups vs placebo in the area under the viral load-time curve (AUC) for influenza virus based on quantification of viral load from nasal swabs

- Descriptive statistics of the area under the viral load-time curve (AUC) for influenza virus based on quantification of viral load from nasopharyngeal swabs by treatment group.
- Descriptive statistics of the time to resolution of viral load and of the peak viral load by treatment group.

The mITT population will be used for the summaries.

9.3.5 *Signs and Symptoms of Influenza*

The difference between VIS410 and placebo will be assessed as outlined below.

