6 DEMOGRAPHICS AND BASELINE CHARACTERISTICS

6.1 Demographics and Baseline characteristics

Descriptive statistics of the general demographic and Baseline characteristics for each treatment group and overall will be presented. Baseline variables age (years), height (cm), weight (kg), body mass index (BMI, kg/m²), both baseline HAI titers (H1 and H3), and time since onset of influenza symptoms will be summarized with n, mean, SD, median, minimum and maximum; time to onset of influenza will also be dichotomized (< 48 hours or ≥ 48 hours) and summarized with counts and percentages. Counts and percentages will be presented for each category of gender, race, ethnicity, vaccination status, confirmed influenza A by method of diagnosis (RAT, PCR, TCID₅₀), and influenza subtype.

The demographic and Baseline data will be summarized in the ITT and mITT populations. All demography and Baseline data will be listed.

The following definitions and conversions will be used:

- Height (in) *2.54 = height (cm)
- Weight (lb) /2.2 = weight (kg)
- BMI = weight (kg)/ height² (m²)
- Time since onset of influenza (hours) = date/time of infusion start – date/time of onset of symptoms. If onset time is missing, it will be imputed as 00:00 on the 24-hour clock.

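### Pooled TCID50 comparisons carry no subtype term although H3 has its own read-out and the read-out for other subtypes is not stated: a modest loss of precision, and no protection if the arms differ in subtype by chance

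*SAP*

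**What the plan says.** SAP 11.2 states that H3 TCID50 samples "will be read out by both hemagglutination and NP-ELISA", and then: "The sensitivity is higher for NP-ELISA; therefore, all viral load parameters will be calculated using the data from NP-ELISA only". The sentence compares two read-outs within H3. No sentence in either document gives the read-out for H1 or any other subtype. SAP 11.2.1 gives one rule for TCID50 values below the limit, with a single example limit (<0.75), and no limit per read-out.

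On the comparison of arms, SAP 11.2 says: "A t-test will be used to assess the difference between treatment groups in the VL AUC and peak VL from nasopharyngeal swabs", based on both qRT-PCR and TCID50, with log transformation or a non-parametric method as fallback. It adds: "Chi-square methods will be used to compare differences in treatment groups relative to placebo for the proportion of subjects with negative results" at Days 3, 5 and 7. Neither test has a subtype term or stratum. Protocol 9.3.4 proposes "One-way analysis of variance (ANOVA) (with treatment group as the factor) or other appropriate statistics detailed in the SAP". On allocation, Protocol 9.2 says "The randomization will be balanced using randomly permuted blocks across the treatment groups" and names no stratification factor.

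Subtype is not absent from the plan. SAP 11.2 summarises viral load by visit, proportion negative, peak and AUC "in the mITT population overall and per influenza A virus subtype". SAP 6.1 tabulates baseline characteristics by arm, "and influenza subtype" among them. SAP 11.3 (time to resolution) gives Kaplan-Meier medians with confidence intervals by treatment group. It has no per-subtype provision and no planned between-arm test.

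**The concern.** A TCID50 value depends partly on how the plate is read. If H3 samples are read by one method and the rest by a less sensitive one, the same amount of virus can give a higher titre, or a detectable instead of an undetectable result, in an H3 subject. A pooled comparison then contains a between-subtype difference that has nothing to do with treatment. A true biological difference between subtypes would add to it or offset it.

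Two things follow. The between-subtype spread sits in the residual variance of the t-test and costs precision. And in the one trial actually run, any difference between arms in H3 share moves the estimated treatment effect by that difference times the between-subtype difference. The per-subtype tables would let a reader see this, but the tests would not correct for it.

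Proportion negative and time to resolution depend directly on the detection limit, so an unstated limit per read-out matters most for them.

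**Working it through.** The plan gives no figure to reproduce: no power calculation, no SD for TCID50 and no expected H3 share.

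**Inputs**
- From the documents: about 150 subjects, 1:1:1, so about 50 randomised per arm; two-sided 0.05; p-values informational only (SAP 4.1).
- Assumed: n = 45 mITT subjects per arm; H3 share p = 0.5, the worst case; within-subtype SD s = 1.5 log10 (1.0 as the low end); between-subtype difference d = 0.5, 1.0 or 1.5 log10. None of these four is in the documents.

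**Formulas**
- SD of the chance difference in H3 share between two arms: √(2p(1−p)/n) = √(2 × 0.25/45) = 0.105, or 10.5 percentage points.
- SD of the resulting shift in the arm difference: 0.105 × d.
- Added variance relative to within-subtype variance: p(1−p)d²/s² = 0.25 d²/s². The standard error grows by √(1 + that) − 1.

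| d (log10) | SD of shift (log10) | Added variance, s = 1.5 | Added SE, s = 1.5 | Added variance, s = 1.0 | Added SE, s = 1.0 |
|---|---|---|---|---|---|
| 0.5 | 0.05 | 2.8% | 1.4% | 6.25% | 3.1% |
| 1.0 | 0.11 | 11.1% | 5.4% | 25% | 11.8% |
| 1.5 | 0.16 | 25% | 11.8% | 56.25% | 25% |

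For scale, the sampling standard error of the arm difference at s = 1.5 is 1.5 × √(2/45) = 0.32 log10. The log10 figures suit peak viral load. The percentages depend only on d/s, so they carry over to AUC for the same ratio. They do not apply to proportion negative or time to resolution, for which nothing was computed.

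**If one subtype dominates.** With p = 0.9, p(1−p) = 0.09. At d = 1.0 and s = 1.5 the added variance is 0.09/2.25 = 4%, or 2% on the standard error.

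**Type I error.** A simulation of 40,000 null trials per setting used 50 per arm, p = 0.5, d of 0.5, 1.0 or 2.0 and s of 1.0, 1.5 or 2.0. It compared the plain t-test with a linear model containing subtype.
- Over all trials: 4.9–5.3% unadjusted and 4.9–5.2% adjusted. The mean bias was essentially zero.
- Among the roughly 6% of trials in which H3 share differed by 20 points or more: unadjusted 5.1–8.4% at d = 0.5, 7.5–15.5% at d = 1.0 and 14–32% at d = 2.0; adjusted 4.5–5.8% throughout.
- The unadjusted standard error exceeded the adjusted one by 0.2% to 40% across settings, and by 5% at d = 1.0, s = 1.5.

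**The case against.** The strongest reply is that a sensitivity difference between subtypes is not documented. A reader might infer that H3 is measured more sensitively than H1, but SAP 11.2 only ranks two methods within H3. Another reading fits as well: H3 gets a second read-out because hemagglutination performs poorly for it, and NP-ELISA brings H3 closer to the rest. Neither the existence nor the direction of a shift can be shown. This stands. What it leaves is that the SAP must say which read-out and limit apply to each subtype. Subtype adjustment remains sensible under either reading, since it also removes any true subtype difference.

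A reader might also infer that pooling biases the treatment comparison. It does not. Under randomisation the expected shift is zero, and the t-test's own variance already contains the between-subtype spread, which is why its level holds. Inflation appears only conditionally, after a sizeable imbalance, and is material only when d is about 1 log10 or more.

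The plan also has partial safeguards. Within a per-subtype summary of a subtype read by one method, the read-out is constant. The baseline table exposes an imbalance, and qRT-PCR, for which no subtype-specific read-out is described, runs in parallel. These make the problem visible but leave the formal comparisons unadjusted, and they do not reach time to resolution.

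Finally, the stakes are low: these are secondary endpoints in a safety study with informational p-values. That lowers the priority but does not remove the point.

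**Conclusion.** The point holds as one of precision, conditional protection and missing specification. H3 has its own TCID50 read-out, the read-out for other subtypes is unstated, and the t-test and chi-square tests pool subtypes with no subtype term.

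Under the assumptions above with s = 1.5 log10, the standard error is larger by about 1% to 12%. A 20-point imbalance in H3 share at d = 1.0 would move the estimate by 0.20 × 1.0 = 0.20 log10, against a sampling standard error of 0.32. All of this scales with a between-subtype difference that the documents do not give, and it fades if one subtype dominates. The documents do not support a claim of systematic bias or of an inflated overall type I error. Priority is modest.

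**What to change.** In SAP 11.2:
- State the TCID50 read-out and detection limit for each influenza A subtype, and align the imputation rule in 11.2.1 with them.
- Compare arms on TCID50 AUC and peak with a linear model containing treatment and subtype. If a non-parametric method is needed, use the van Elteren test stratified by subtype.
- Compare the TCID50 proportion negative with Cochran-Mantel-Haenszel by subtype.

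In SAP 11.3, present the TCID50 Kaplan-Meier medians by subtype as well as overall, and stratify by subtype any exploratory between-arm test. No such test is planned now, so there is nothing else to stratify.

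Optionally, if other subtypes turn out to be read by hemagglutination, repeat the TCID50 comparisons with the H3 hemagglutination data, which are generated anyway.

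The cost is SAP wording and a few lines of code, since subtype is already collected and tabulated. Randomisation need not change. The one complication is subjects with unknown or mixed subtype: they need a stratum of their own, defined before unblinding.
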